4.4 Endpoints

Primary Endpoint: The primary outcome measure will be the proportion of major hip injuries due to fall in the subjects receiving SOC as compared to subjects receiving SOC plus the Tango Belt.

Secondary Endpoints: Secondary outcome measures include the proportion of each of the following:

- Hip fractures due to fall in the subjects receiving SOC as compared to subjects receiving SOC plus the Tango Belt.
- Emergency Department visits due to fall in the subjects receiving SOC as compared to subjects receiving SOC plus the Tango Belt.
- Hospitalizations due to fall in the subjects receiving SOC as compared to subjects receiving SOC plus the Tango Belt.

Ancillary Endpoints: Ancillary endpoints will include:

- Adverse events
- Major injuries due to fall
- Fall occurrence
- Device wear adherence
- Device fall alerts
- Device discrimination of serious hip-impacting vs. non-serious hip and non-hip impacting falls
- Airbag deployment
- FES-I short version

5. Selection of Subjects

- **5.1 Inclusion Criteria**: All subjects are required to meet ALL of the following inclusion criteria to be considered eligible for participation in this study:
 - 1. Age 65 years or older;

- 2. Have experienced a fall-related fracture after age 50 -OR-
 - Have experienced one or more falls in the 12-months prior to consent and have a diagnosis of osteoporosis, osteopenia, or prescribed osteoporosis medication.
- Independently or with staff or caregiver assistance, able to transfer between surfaces (e.g., to or from a bed, chair, wheelchair, toilet, standing position) or walk or move between locations (use of an assistive device such as a walker is acceptable);
- 4. Have a waist circumference between 29 50 inches (63.5 127 cm);
- 5. Able to comply with required study procedures and follow-up schedule as determined by the Study Investigator;
- 6. Are under the care of the Investigational organization;
- 7. Provides consent or their legally authorized representative provides consent on subject's behalf
- **5.2 Exclusion Criteria**: Subjects will be excluded from participating in this study if they meet ANY of the following exclusion criteria:
 - 1. Age 64 years or less;
 - 2. Participation in a different clinical investigation that can conflict with this clinical study as determined by the Study Investigator and approved by the Sponsor;

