5.3 Strategies for Recruitment and Retention

Control group: The investigator or designee will retrospectively review the site's EMR database to determine their long-term care patient population's initial eligibility for meeting the study inclusion criteria. The subjects in the clinical site census at the time frame 6 months prior to the IRB approval date will be screened for eligibility for study inclusion. Subjects eligible for the control group must meet the requirements of the inclusion and exclusion criteria except for the waist circumference and need for consent. Eligible subjects' electronic health records will be mined for the baseline, midpoint, and

final study metrics. If there is an insufficient number of eligible subjects to meet the control group target (defined as 4 times the expected number of intervention group subjects to be enrolled from the site) at 6 months prior to the intervention group start date, the EMR database screen will extend retrospectively in 6 month increments until the control group target is reached.

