Intervention group: The investigator or designee will review the site's EMR database to determine their current long-term care patient population's initial eligibility for meeting all study inclusion and exclusion criteria, except for waist circumference, informed consent, and ability to comply. Subjects meeting initial eligibility will then have their waist circumference obtained, and those that meet inclusion criteria will then be offered the opportunity to participate in the study through the informed consent process utilizing IRB approved subject facing recruitment materials including a video introduction of the device, a flyer on the device and research study and verbal explanation of the study with access to study site investigator for addressing questions and/or concerns. If the subject agrees to be a participant in the study, the subject will be given a written informed consent to read, sign and date (Appendix 1 - Informed Consent). If the subject has a Legally Authorized Representative (LAR) or Person of Authority (POA) in place, the POA will receive notification regarding the eligibility for the subject to participate in the study with the IRB approved subject facing recruitment materials including video introduction of the device, a flyer on the device and research study and verbal explanation of the study with access to study site investigator for addressing questions and/or concerns with the written informed consent. The POA may offer consent verbally over the phone to the investigator/ designee with notation on the Informed Consent Form and subsequent receival of copy of the ICF via USPS or email. The ICF can also be signed electronically with a provided eSignature option to the POA. All subjects or POAs will be given the opportunity to discuss the technology, risks, potential benefits, alternative therapies, and the study requirements with the investigator prior to signing the informed consent. Subjects or their POAs that provide written or electronic consent will be preliminarily enrolled into the intervention group.

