Upon preliminary enrollment, utilization of the Tango Belt will be prescribed by the site's physician and written into the subjects' plan of care at the care residence. A Tango Belt of appropriate size based upon waist measurement will be provided to the subject by the investigator or designee. The subject will be assigned to the Tango Belt ID located in the APT cloud electronically via Tango Belt companion app for data tracking. The Tango Belt size will be adjusted for most comfortable and appropriate fit using the sizing strap located in the left side zipper pocket of the Tango Belt. The Tango Belt will be prescribed to be worn up to 24 hours/ day with removal for bathing activities, dressing as needed, twice a week at minimum for charging and upon subject request. Baseline metrics will be obtained from the subjects' EMR. The enrolled participant will be

assessed for cognition level via the BIMS if this has not already been taken as part of the EMR. Assessment of balance confidence using the short version of the FES-I if they are cognitively capable of completing the survey with a BIMS Score of 13-15. (Appendix 2 – Study Questionnaire)

Enrolled subjects in the intervention group will then proceed through a run-in period of 14 days to assess adherence to utilization of the Tango Belt. At 14 days, if the subject is demonstrating adherence to use of the device of at least 64% as viewed by the investigator or designee in the Tango Belt companion app dashboard as "Compliance" (defined as wearing the device for at least 1 hour per day for at least 9 of 14 days), they will be fully enrolled into the study and proceed through the study duration. Subjects who do not meet the run-in period requirement will be withdrawn from the study.

Screen Failures in this study would include study candidates that:

- Do not meet inclusion criteria
- Meet any exclusion criteria
- Do not fit within the range of Tango Belt sizing available
- Do not comply with the minimum device utilization of 64% within the run-in period

To account for the relatively high morbidity and mortality of the target study population, we will assume a 20% in-study attrition rate, and thus will aim to over-recruit by this amount beyond the target sample size statistically required for the intervention group.

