6.1 Device

The Tango Belt (the "Device") is a wearable belt designed to enable safer mobility of geriatric individuals (≥ 65 years of age) at risk for fall injury by mitigating major hip injuries due to falls. The Tango Belt is a patient-contacting electronic device made out of medical grade plastics and biocompatible fabrics. It is worn around the waist at the iliac crest, secured by a buckle. It comes in 5 sizes, XS, S, M, L, and XL, to accommodate wearers with a waist circumference between 29-50 inches (covering the 5th-95th percentile of older adults in the US); each belt is further adjustable to prevent sliding past the hips or elevating out of position.

The Tango Belt contains a fall-in-progress detection algorithm which can detect a serious hip-impacting fall-in-progress using built-in sensors and deploy an automotive-grade cold-gas airbag to protect the hips from ground impact forces. When connected to Wi-Fi, the Tango Belt can send automated fall and impact alerts to caregivers and Healthcare Providers (HCPs) while recording motion and event data, which can then be analyzed for usage-based metrics viewable via a companion mobile app and/or desktop app. The Tango Belt can also send manually activated alerts for help, triggered by pressing a button on the belt buckle, when connected to Wi-Fi. Alerts are sent in the form of SMS texts and emails to alert recipients designated in the mobile or desktop Companion App. The Tango Belt can also detect non-serious hip-impacting or non-hip impacting falls in which the wearer may have incurred a minor injury (i.e., not a major hip injury) and/or may be unable to get up.

Additionally, the belt can be periodically surface disinfected using a germicidal wipe. Further, the belt contains a non-replaceable lithium-ion battery, which requires recharging via the included specially designed AC adapter every several days depending on wear duration. An optional Safety Latch can be installed by care staff on any belt to prevent inadvertent unbuckling. Lastly, if airbag deployment occurs, the Tango Belt cannot be reused.

The Tango Belt's Companion App (available in mobile and desktop versions) enables the following added functionality: 1) connecting the belt to Wi-Fi (mobile version only), 2) inputting contact information for alert recipients, 3) viewing dashboard metrics (e.g. Compliance and Daily Wear), 4) taking or administering the FES-I survey, and 5) managing a fleet of multiple belts within a facility setting.

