5 ANALYSIS POPULATIONS

5.1 HISTORICAL CONTROL POPULATION

The Historical Control Population (HC) for this study includes retrospective subjects that meet all inclusion and exclusion criteria except for the waist circumference and need for consent. Eligible subjects' electronic health records will be mined for the baseline, midpoint, and final study metrics.

The investigator or a designee will retrospectively review the site's electronic medical record (EMR) database to determine long-term care patient population's eligibility for meeting the study inclusion criteria. The subjects in the clinical site census at the time frame 6 months prior to the IRB approval date will be screened for eligibility for study inclusion.

If there is an insufficient number of eligible subjects to meet the control group target (defined as 2 times the expected number of intervention group subjects to be enrolled from the site) at 6 months prior to the intervention group start date, the EMR database screen will extend retrospectively in 6 month increments until the control group target is reached.

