7.1 Propensity Score Method

For each subject, a PS (i.e., predicted probability between 0 and 1) of intervention group membership (Tango Belt vs. SOC) will be calculated using a logistic regression, with "intervention group" as the outcome and the following baseline variables as the predictors: Age, mobility level, sex, and whether the subject fell in the past year.

Once propensity scores are calculated, propensity score matching (PSM) without replacement will be performed.

Subjects in the intervention group (i.e., Tango Belt) will be matched to controls with a similar PS using nearest neighbor matching (NNM) at a ratio of 1:2.

The PS modeling and design will be performed by a statistician who will be blinded to the endpoint data for each subject to avoid introducing bias into the analysis. The blinded endpoint data includes the primary and three secondary endpoints listed in section 3.2.

Balance of baseline variables (e.g., continuous variable, dichotomous variable, interaction terms, or squares of continuous variable) will be assessed by comparing the pre-matched and post-matched datasets.

Adequacy of propensity balance will be assessed by examination of standard differences between groups to confirm standard difference in post-matched dataset does not exceed 10%. Additionally, a comparison of the baseline covariate variables between groups after adjusting for propensity subgroup will be carried out as in D'Agostino et al. If the propensity matching is adequate, this will result in non-significant p-values (p>0.05) for the baseline characteristics.

Additional PS methods may be employed if group balance is not achieved by NNM, examples include covariate adjustment, inverse probability of treatment weighted (IPTW), etc.

Since enrollment may be ongoing at the time of interim analysis, propensity score modeling and matching will be conducted at the interim analysis and subjects will be rematched at the time of the final analysis to ensure the best PS match possible. With PS matching possibly occurring twice the following differences in PS modeling and design may occur:

- 1. Subjects may be matched to different control subjects.
- 2. The number of matches (1:1 or higher to a maximum of 1:4) may change based upon enrollment ratios.

3. The technique used to match (i.e., NNM) may change to another PS method to ensure adequacy of propensity balance.

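### Residents outside the belt's waist range can enter only the control group, and no body-size variable in the matching, balance check or outcome model measures or adjusts for this

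*Combined protocol and SAP*

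**What the plan says.** - **Belt group.** Protocol 5.1 requires: "Have a waist circumference between 29 50 inches (63.5 127 cm". Protocol 5.3 has waist measured after the record screen ("Subjects meeting initial eligibility will then have their waist circumference obtained") and lists among screen failures those who "Do not fit within the range of Tango Belt sizing available".
- **Control group.** Protocol 5.3 applies every criterion except "for the waist circumference and need for consent". SAP 5.1 agrees: controls are "retrospective subjects that meet all inclusion and exclusion criteria except for the waist circumference and need for consent". Nothing replaces the waist criterion.
- **Share outside the range.** Protocol 6.1 describes belt sizes for "wearers with a waist circumference between 29-50 inches (covering the 5th-95th percentile of older adults in the US".
- **Adjustment.** The propensity predictors in SAP 7.1 are "Age, mobility level, sex, and whether the subject fell in the past year". The primary and secondary models (SAP 7.2, 7.3) compare groups with control for that score only. If balance fails, SAP 7.1 allows another propensity technique but names no further covariate. Waist, weight and BMI are also absent from the baseline summary (SAP 6.6) and the imputation model (SAP 6.3.1).
- **Control pool.** SAP 5.1 targets 2 controls per expected belt subject. SAP 7.1 matches 1:2 by nearest neighbor without replacement and states no caliper.

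**The concern.** The eligibility rules differ between the groups on a physical characteristic that could bear on hip injury. A very thin or very large resident counts in the control rate but can never count in the belt rate.

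Matching is unlikely to remove these controls. With a pool target of 2 per belt subject and a 1:2 match without replacement, nearly every usable control is taken. The 10% standardized-difference check can pass while the groups differ on size, because size is not among the variables it sees.

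At stake is whether part of any observed reduction reflects who could wear a belt, not what the belt does. As the SAP stands, that part cannot be estimated after the fact either.

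**Working it through.** **1. The plan's own figures.** These fix the sample size and event rate for the check.
- Pocock-type spending at half the information gives a nominal one-sided interim alpha of 0.025 × ln(1 + (e − 1) × 0.5) = 0.0155, and 0.0139 at the final look.
- With continuity correction and 1:2 allocation, 15% vs 3% needs 94 belt subjects (SAP: 94). 15% vs 6% needs 185 (SAP: 188).
- These figures reproduce only if 15% is the six-month proportion. SAP 4.1 calls 15% annual with six months of follow-up, or about 7.5%, and the same formula then gives 198 and 392. That is a separate issue, so both rates are used below.
- 188/0.7 = 268.6 and 376/0.7 = 537.1, so the SAP's 268 and 536 are enrolment numbers inflated for attrition. The check uses 188 vs 376.

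**2. Inputs.**
- Share of controls below the range, f₁ = 5%, and above it, f₂ = 5% (protocol 6.1, general older adults).
- Risk of out-of-range relative to in-range residents: R₁ (thin) and R₂ (large). These are not in the documents and are assumed.
- Control rate pC = 15% or 7.5%. The 15% was observed in controls, a group that may already include out-of-range residents, so it is the mixed rate.

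**3. Formulas.** Let D = 1 − f₁ − f₂ + f₁R₁ + f₂R₂. The in-range rate, which an inert belt would show, is pT = pC/D. The spurious reduction is 1 − 1/D. The rejection rate with no belt effect is Φ[((pC − pT) − 1.96·SE₀)/SE₁], where SE₀ is the pooled and SE₁ the unpooled standard error at 188 vs 376.

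Example for R₁ = 1.5, R₂ = 1, pC = 15%: D = 1.025 and pT = 14.63%. SE₀ = 0.03179 and SE₁ = 0.03168. (0.00366 − 0.06231)/0.03168 = −1.851, so the error is 3.2%.

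**4. Results.**

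| R₁ thin | R₂ large | D | Spurious reduction | Error, 15% | Error, 7.5% |
|---|---|---|---|---|---|
| 1.5 | 1 | 1.025 | 2.4% | 3.2% | 2.9% |
| 2 | 1 | 1.050 | 4.8% | 4.0% | 3.4% |
| 2.5 | 1 | 1.075 | 7.0% | 5.0% | 4.0% |
| 2 | 2 | 1.100 | 9.1% | 6.1% | 4.5% |
| 2 | 0.5 | 1.025 | 2.4% | 3.2% | 2.9% |
| 1.5 | 0.5 | 1.000 | 0% | 2.5% | 2.5% |
| 1 | 0.5 | 0.975 | −2.6% | 1.9% | 2.1% |

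In the thin-only cases a true 60% effect would appear as 1 − 0.4/1.025 = 61.0% to 1 − 0.4/1.075 = 62.8%.

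The error rates are normal approximations for a single unadjusted test at 0.025. They ignore the interim look and the propensity adjustment.

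**5. Unit check on the limit.** 50 in × 2.54 = 127.0 cm, which agrees with the printed figure. 29 in × 2.54 = 73.7 cm, but 63.5 cm is printed, and 63.5/2.54 = 25.0 in. The synopsis and protocol 5.1 both carry this mismatch. The percentile statement in protocol 6.1 is tied to 29 in. If 63.5 cm were applied, the share below the limit would be under 5%.

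**The case against.** - **Direction.** No section gives hip-injury risk by body size. A reader might infer that the bias favours the belt because thin residents have less padding. That is an assumption, and the same argument would give large residents a lower risk, which offsets it. This objection stands: the direction is not established.
- **Size.** A reader might suppose that many frail long-term-care residents fall below the limit, say 15% at a risk ratio of 2.5, which gives 1 − 1/1.225 = 18%. The documents give no such share, only about 5% per tail, and that for older adults in general. Error rates computed at 268 vs 536 would also overstate the problem, because those numbers include the attrition allowance. This stands too.
- **Practicality.** Waist is obtained only after the record screen, so it could not readily be applied to past records. That explains the waiver, but it does not explain the absence of any substitute for waist.
- **Partial adjustment.** Age, sex and mobility may capture some of body size. How much is unknown, and nothing in the plan would show it.
- **Small pool.** Removing controls by BMI from the primary analysis could break the 1:2 match. SAP 6.2.2 already drops controls with missing information. This stands and shapes the fix.

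**Conclusion.** The structural point holds. Out-of-range residents can enter only the control group, and no body-size variable is in the propensity model, the balance check or the outcome model.

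The likely effect is modest. With 5% of controls too thin and an assumed risk ratio of 1.5 to 2.5 for them alone, the spurious reduction is 2.4% to 7.0%. The one-sided error is then about 3.2% to 5.0% at a 15% control rate, or 2.9% to 4.0% at 7.5%. With lower risk in large residents the bias shrinks, cancels or reverses to about −3%.

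Two stronger readings are not supported. The documents do not show that the bias favours the belt, and no plausible value here comes near the 60% to 80% effects the trial is sized for. How many controls are actually out of range is also unknown. The point is worth correcting because the imbalance is currently unmeasured and the correction is cheap.

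**What to change.** - **SAP 5.1:** extract the last height and weight before the index date for both groups. The documents do not say that the EMR or MDS holds them, so confirm this first.
- **SAP 7.1:** add BMI, or weight if height is poorly recorded, to the propensity model and to the 10% standardized-difference check. The statistician blinded to endpoints should specify this before matching.
- **Sensitivity analysis:** prespecify one that excludes controls whose BMI lies outside the range seen in belt subjects. Keep them in the primary analysis, because the pool has little to spare.
- **SAP 6.2.2:** state how missing height or weight is handled, for example with a missing category. Otherwise controls without a recorded weight are lost.
- **Synopsis and protocol 5.1:** reconcile the inch and centimetre values of the lower waist limit, and make protocol 6.1 agree.

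The cost is two more fields per subject and some SAP wording. BMI is only a proxy for waist, so some difference may remain.

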5.2 Intervention Population

Propensity score matching (described in section 7.1) will be used to match each treatment group subject with two subjects from the historical control group. If a subject from the treatment group is not included in any of the analysis populations described below, the historical control subjects they matched to using propensity scores will also not be included in any analysis comparing groups.

5.2.1 INTENT TO TREAT POPULATION (ITT)

The ITT population will consist of all intervention population subjects who demonstrate at least 64% adherence to use of device during run-in period (defined as wearing device for at least 1 hour per day for at least 9 of 14 days) and the propensity matched historical controls.

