 Metrics of the compliance to wear of the Tango Belt by the subject defined as at minimum 64% (at least 1 hour a day for 9 days out of 14) will be provided by sponsor to the CRA. If the subject is not utilizing the device for at least the minimum amount of time, they will be determined to be a screen failure and withdrawn.

Visit 3 Midterm (90 days +/- 10):

- Metrics of changes in fall mitigation plan, mobility level and fall events including falls, falls with major injury, adverse events (whether not pertaining to the Tango Belt), emergency department visits, and hospital admissions will be taken by the site investigator or designee research assistant directly from the MDS and/or EMR within the electronic documentation system utilized at the clinical study site.
- Metrics of Tango belt wear days and wear hours/day will be provided to the site investigator or designee research assistant from the sponsor or obtained from the Tango Belt Companion App.
- Metrics of device deficiencies, device discrimination between types of falls, airbag deployments, and alerting will be provided to the site investigator or designee research assistant by sponsor from the Tango Belt cloud.

End of Study (180 days +/- 30):

 Metrics of changes in fall mitigation plan, mobility level and fall events including falls, falls with major injury, adverse events (whether or not pertaining to the Tango Belt), emergency department visits, and hospital admissions will be taken by the site -

- investigator or designee research assistant directly from the MDS and/or EMR within the electronic documentation system utilized at the clinical study site.
- Metrics of Tango belt wear days and wear hours/day will be provided to the site investigator or designee research assistant by sponsor or obtained from the Tango Belt Companion App.
- Metrics of device deficiencies, device discrimination between types of falls, airbag deployments, and alerting will be provided to the site investigator or designee research assistant by sponsor from the Tango Belt cloud.
- Tango Belt will be collected by the sponsor for return to Active Protective Technologies, Inc.

Unscheduled Visit (AE, hospitalization, change in status in medical care plan):

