3.2 STUDY ENDPOINTS

3.2.1 PRIMARY ENDPOINT

The study's **primary effectiveness endpoint** is the proportion of major hip injuries due to fall in the subjects receiving SOC as compared to subjects receiving SOC plus the Tango Belt, as reported between enrollment and the 180-day visit.

There is no primary safety endpoint for this study. Safety of the device will be determined by analysis of adverse events as an ancillary endpoint.

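### The belt group's 'ITT' set admits only residents who passed the 14-day wear run-in, controls face no matching day-14 condition, and day 0 is not fixed in either group, so an inert belt could show apparent benefit

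*Combined protocol and SAP*

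**What the plan says.** **Belt group.** Under protocol 5.3, consented residents "will be preliminarily enrolled into the intervention group", are prescribed and given a belt, and then enter a 14-day run-in. Those who pass the wear test are handled as follows: "they will be fully enrolled into the study and proceed through the study duration". For the others, "Subjects who do not meet the run-in period requirement will be withdrawn from the study". Protocol 7.3 (Visit 2) adds that "they will be determined to be a screen failure and withdrawn". SAP 5.2.1 makes passing the test the condition for the ITT set, which on the belt side consists of "all intervention population subjects who demonstrate at least 64% adherence to use of device during run-in period", with adherence "defined as wearing device for at least 1 hour per day for at least 9 of 14 days". The per-protocol and adherence sets (SAP 5.2.2, 5.2.3) are subsets of it. Run-in failures remain only in the Safety population (SAP 5.2.4).

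**Controls.** SAP 5.1 admits residents from a site census about 6 months before IRB approval, or from earlier 6-month blocks. They must meet the eligibility criteria apart from waist size and consent. No run-in, day-14 condition or index date per control is given.

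**Clock.** SAP 3.2.1 counts the primary endpoint "as reported between enrollment and the 180-day visit". For the belt group this could mean preliminary enrollment (protocol 5.3), full enrollment after the run-in (also 5.3), or belt provision, where protocol 6.5 starts the 6 months.

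**Adjustment.** The propensity score in SAP 7.1 uses age, mobility level, sex and a fall in the past year.

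**The concern.** A population called intent-to-treat should not depend on what happens after assignment. Here it does, in the belt group only. A resident who breaks a hip on day 6 and goes to hospital has at most about 6 wear days. That resident is very unlikely to reach 9, is reclassified as a screen failure and takes a primary event out of the belt numerator. Death or transfer in the first days has the same effect on the denominator. Residents who will not or cannot keep a device on are also removed, and nothing in the propensity score measures that trait.

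Later steps do not restore these residents. Multiple imputation (SAP 6.3) is confined to the ITT set. The schedule in protocol 7.2 has no fall or adverse-event capture at the run-in visit, so a resident withdrawn at day 14 has no later scheduled efficacy read. The ITT set carries the primary test (SAP 6.3, 7.2) and the three secondary tests (SAP 7.3). The comparison is not randomised, so a positive result could partly reflect who was allowed into the belt group.

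**Working it through.** **Inputs from the documents:** 188 belt and 376 control subjects evaluable at the final analysis (SAP 2); one-sided 0.025 (SAP 4, 7.2); 14-day run-in inside a nominal 180 days; a 15% control figure.

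**Inputs assumed:** the share f failing the run-in, and the injury risk r of failures relative to passers after matching. The documents give neither.

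**Step 1. Which risk does the plan use?** SAP 4 calls 15% a proportion of subjects. SAP 2 and 4.1 call it an annual rate, which is about 7.5% over 6 months. The plan's sample sizes can be tested against both, using a continuity-corrected two-proportion formula at 1:2, 80% power and Pocock-type spending of 0.025 at half information.
- Interim (one-sided 0.0155), 15% vs 3%: 94 belt subjects. Stated: 94.
- Final (one-sided 0.0139), 15% vs 6%: 185. Stated: 188.
- Attrition: 94/0.7 = 134.3 and 188/0.7 = 268.6. Stated: 134 and 268.
- With 7.5% as the 6-month risk, the same formula gives 198 and 392.

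The stated sizes fit 15% as the risk over follow-up, while the text twice calls it annual. Those passages need reconciling. Both readings are carried below.

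**Step 2. Time window alone, inert belt.** Suppose belt events count from day 14 to 180 and control events from day 0 to 180, with constant hazard. The belt risk is then 1 − (1 − p)^(166/180).
- p = 15%: 1 − 0.85^(166/180) = 13.92%, ratio 13.92/15 = 0.93.
- p = 7.5%: 1 − 0.925^(166/180) = 6.94%, ratio 0.92 to 0.93.
- Control risk in the unmatched 14 days: 1 − 0.85^(14/180) = 1.26%, or 1 − 0.925^(14/180) = 0.60%. Among 376 controls that is 4.7 or 2.3 events.

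**Step 3. Selection alone, inert belt, common window.** The assigned group's risk is p = (1 − f)q + f·r·q, where q is the risk in passers. The apparent risk ratio is therefore q/p = 1/(1 − f + f·r). For f = 0.2:
- r = 1.5: 1/1.1 = 0.91
- r = 2: 1/1.2 = 0.83
- r = 0.75: 1/0.95 = 1.05

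**Step 4. False-positive rate.** Exact rejection probability of an unadjusted pooled z-test, 188 vs 376, one-sided 0.025. The planned test is a propensity-adjusted logistic regression, so these are approximations.

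| Scenario (inert belt) | Risk ratio | 15% six-month risk | 7.5% six-month risk |
|---|---|---|---|
| No bias | 1.00 | 2.3% | 2.2% |
| Window only | 0.93 | 4.9% | 3.7% |
| Selection, f = 10%, r = 1.5 | 0.95 | 3.9% | 3.1% |
| Selection, f = 20%, r = 1.5 | 0.91 | 5.9% | 4.1% |
| Selection, f = 20%, r = 2 | 0.83 | 11.7% | 6.8% |
| Selection, f = 30%, r = 2 | 0.77 | 19.3% | 10.2% |
| Selection, f = 20%, r = 0.75 | 1.05 | 1.3% | 1.5% |

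The window and selection rows should not be multiplied together. Early injury is one reason for failing the run-in, so stacking them partly counts the same loss twice.

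**The case against.** The run-in is openly specified, and requiring tolerance of a wearable device is a legitimate design choice. Protocol 5.4 records date, reason and prior data for every screen failure, and SAP 6.6 tabulates the Safety population's baseline beside the ITT and control sets. None of this is an effectiveness analysis.

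The control side is not free of selection. Ability to comply is nominally an eligibility criterion for controls too. Protocol 5.4 withdraws any subject who stops meeting the criteria. SAP 6.2.2 leaves out controls with missing information, which may remove some who died or left early. These rules weaken any claim that losses fall on one group only, but none is a 14-day wear or early-injury condition.

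SAP 5.2 also drops the controls matched to an excluded belt subject. That does not cure the problem. It removes controls because of their propensity score, not because they were injured early or would have refused a belt. It may not even apply to run-in failures, who stay in the Safety population.

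Three stronger readings are tempting, and the documents do not support them:
- *That controls are counted from their first day.* SAP 5.1 gives a census time frame and no index date per control.
- *That every early belt injury or death is lost.* Only events that prevent 9 wear days are sure to be lost. A resident injured or dying on days 10 to 14 may already have passed. Whether a passer's run-in injury counts depends on which enrollment SAP 3.2.1 means.
- *That an inert belt would show benefit.* This needs either the unfavourable reading of day 0 or failures at higher risk than passers. The second is plausible but not shown, and at r = 0.75 the ratio is 1.05.

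**Conclusion.** The set named ITT is conditioned on post-assignment behaviour in the belt group, and controls have no corresponding condition. No effectiveness analysis of all belt-assigned residents stands beside it. That follows from the text and needs no assumption.

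The size does rest on assumptions. The window part (ratio about 0.93) arises only if belt events start at day 14 and control events at day 0. It largely disappears if belt events count from belt provision, or for a full 180 days after the run-in. The selection part (0.91 to 0.83 for 20% failing at 1.5 to 2 times the risk) depends on a failure share and a direction that the documents do not supply. The supportable statement is that an inert belt could show apparent benefit, with a false-positive rate of roughly 4% to 12% in these scenarios. For a pivotal non-randomised comparison this should be corrected before the analysis.

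**What to change.** 1. **Put both groups on one clock.** Define day 0 as belt provision, and as a stated census index date for each control. Start counting endpoints at day 14 in both groups, over the same follow-up length. Require controls to be alive, resident and free of major hip injury at their day 14, and hold belt subjects who passed the run-in to the same condition.
2. **Name the set for what it is.** Call the SAP 5.2.1 set 'run-in completers' or modified ITT, and limit the primary claim to residents who accept the belt.
3. **Show the excluded residents.** Report the number of run-in failures and their injuries. Add a secondary all-assigned analysis (everyone given a belt, from day 0, against controls from day 0) using records already at the sites, for those who have not withdrawn consent.

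Item 1 removes only the time-window part. Items 2 and 3 address selection.

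**Cost.** Items 1 and 2 are SAP text plus an index date and a date filter on the control data. They drop about 0.6% to 1.3% of controls for early events. Item 3 is more than SAP wording: reading records of run-in failures after withdrawal needs a protocol amendment and IRB review. The all-assigned estimate is likely to be less favourable, and the trial is not sized for it. If failures get no protection, the detectable interim effect falls from 80% to 80% × (1 − f). The formula that gives 94 then needs 120 belt subjects at f = 10% and 156 at f = 20%. That is a reason to keep this analysis secondary.
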